
• doesn't have a well visit scheduled in the next 45 days• has not had a well child visit > 365 days	
• doesn't have a well visit scheduled in the next 45 days• has not had a well child visit in 365 days

• have English and/or Spanish as preferred language	• have English and/or Spanish as preferred language
---	---

Factors under study (levels):

Personal Contacts (12-14 month & 4-year-olds) Trial:

Number of automated messages sent prior to any personal contact attempts (1 vs. 2)

Number of personal contact attempts made by medical assistant (0 vs. 1)

	1 automated message sent	2 automated messages sent
0 personal contact attempt		
1 personal contact attempt		

MyChart Trial:

Families enrolled in MyChart will be selected and randomized into the following groups:

	no message	1 MyChart message sent	2 MyChart messages (e.g. Mon and Thurs)
Low Tailored Message			
High Tailored Message			

Number of messages (0 vs. 1 vs. 2); Type of messages (low tailored message with name only vs. high tailored message with date of last WCC and age included)

Televox (age 6-11yo) Trial:

Patients will be randomized into the following three groups. Patients with MyChart are excluded:

no message	Low Tailored Message 2 automated standard messages sent (e.g. Thu, Fri)	High Tailored Message 2 automated tailored messages sent (e.g. Thu, Fri)
------------	--	---

Televox (age 12-17yo) Trial:

Patients will be randomized into the following three groups:

no message	Low Tailored Message 2 automated tailored messages sent (e.g. Thu, Fri)	COVID Tailored Message 2 automated messages sent (e.g. Thu, Fri)
------------	--	---

Automated Message: Parents indicate their preferred mode of reminder (e.g. call or text message) when they schedule appointments. Cincinnati Children's uses a HIPAA compliant platform called TeleVox to send automated calls and text reminders to parents according to their preferences which are recorded in the Electronic Health Record (EHR).

Here is the script for **low tailored automated messages** that will be sent via call or text:

Clinic	Message 1*	Message 2*
---------------	-------------------	-------------------

HPC	Hi! Hopple misses you! (INSERT FIRST NAME) is due for a checkup. Please call [contact], option 1 to schedule a visit as soon as possible.	Hi! If you haven't already, please call [contact], option 1 to schedule (INSERT FIRST NAME)'s upcoming visit at Hopple.

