PPC	
Hi, this is [Staff First Name] from PPC. [Pt first name] is due for a check up. I'll call in a day or two to help schedule that appointment or you can walk in today to have your child seen! You can also call [contact], option 1 to schedule.
	
Hi, this is [First Name] from PPC. I noticed that [Child's First Name] is due for a check up. Can I schedule that for your right now?
 
Alternate script for leaving a voice message: Hi, this is [First Name] from PPC. I noticed that [Child's First Name] is due for a check up. Sorry I missed you. Please call [contact], option 1 to schedule your appointment or walk in today to have your child seen.

*Scripts have been translated into Spanish versions by Interpreter Services

Response variables (outcomes):

- Appointment **was scheduled** within 2 weeks of intervention (Y/N) (date of actual appointment may be greater than 2 weeks from intervention)
- Appointment **was completed** within 8 weeks of intervention (Y/N). Appointment completed within 8 weeks of randomization will be used for group who does not receive any intervention.
- (Primary Outcome) Receipt of MMR by 15 months of age or receipt of 2nd MMR dose by 3 months after randomization (Y/N)
- Receipt of 1st COVID vaccination (ages 12-17 years) within 8 weeks of first intervention (Y/N)
- Family member receipt of COVID vaccination in our health system within 8 weeks of first intervention

Blocking: (controlling for factors that might influence the outcome)

- Age (12-14 months, 4 years)
- Clinic location (PPC, HPC, FPC)

Personal Contacts (12-14 months & 4-year-olds) Trial:

Randomization: Eligible patient will be identified by running a report in the electronic health record (EHR). We will run this report, stratified by clinic location, and randomly assign patients into one of the four groups created by our 2 X 2 design. Groups will receive their assigned intervention in one of four successive weeks with the sequence randomly assigned (see table below).

Replication: We will conduct a total of 3 trials, repeating the randomization procedure every 4 weeks to identify children who become eligible: Weeks 1-4 = trial #1, weeks 5-8 = trial #2, weeks 9-12 = trial #3.

	1 automated message sent	2 automated messages sent
--	---------------------------------	----------------------------------

0 personal contact attempt	Message sent on Thu (weeks 3, 5, 10)	Message sent on Thu & Fri (weeks 4, 6, 12)

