1 personal contact attempt	Above plus attempt Mon – Fri of following week (weeks 2, 7, 11)	Above plus attempt Mon – Fri of following week (weeks 1, 8, 9)

MyChart and Televox Trials (6-17 years old):

Randomization: Eligible patients will be identified by running a report in the electronic health record (EHR). We will run this report, stratified by clinic location, and randomly assign patients into one of the study groups as described above. Groups will receive their assigned intervention in one of four successive weeks with the sequence randomly assigned (see table below).

We will randomize children who are eligible and implement interventions for each trial : Weeks 1-3 = Televox Trial 12-17yo, Weeks 4-7 = Televox Trial 6-11yo, Weeks 8-10 = MyChart Trial.

MyChart Trial:

	no message	1 MyChart message sent	2 MyChart messages (e.g. Mon and Thurs)
Standard Message	No intervention	Week A	Week B
Tailored Message		Week A	Week B

Televox (6-11yo) Trial:

no message	Low Tailored Message 2 automated standard messages sent (e.g. Thu, Fri) (weeks C, C)	High Tailored Message 2 automated tailored messages sent (e.g. Thu, Fri) (weeks D, D)
-------------------	---	--

Televox (12-17yo) Trial:

no message	Low Tailored Message 2 automated tailored messages sent (e.g. Thu, Fri) (week A)	COVID Tailored Message 2 automated messages sent (e.g. Thu, Fri) (week B)
-------------------	---	--

Of note, automated messages and/or personal contact attempts will not be completed if the parent schedules an appointment after being randomized but before receiving the intervention.

Covariates for logistic regression: (factors that might influence the outcome if not be balanced across groups)

1. Child age at the time of randomization (rationale: visits are less frequent for children age 4 years)
2. Parent preference for call vs. text mode of contact (rationale: calls may be more likely to get blocked than texts)
3. Parent with activated MyChart account (Y/N) (rationale: not dependent on calling scheduling center to make appointment)
4. Access to appointment: Number of days to 3rd next available appointment at patient's clinic at time their first automated message is sent
5. Patient receipt of any past immunizations (Y/N) (rationale: vaccine refusing parents will be unlikely to change even if they return for well child check)

6. School-age vs. adolescent patient age (rationale: adolescents less likely to get yearly check-ups)
7. Historical no-show rate

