For the Personal Contact (12-14 mo & 4 years old) trials, we will conduct intent-to-treat analyses using logistic regression models (without adjusting for covariates) for each of our three binary outcomes: completed appointment

within 2 weeks, completed appointment within 8 weeks, receipt of MMR by 15 months of age or receipt of 2nd MMR by 3 months after randomization. We will do pair-wise comparison among the 4 groups and adjust p value of each comparison for multiplicity. If participants in the 4 groups differ on potential covariates, we will conduct additional analyses adjusted for these variables.

For the MyChart and Televox Trials (6-17 years old), we will conduct intent-to-treat analyses using logistic regression models (without adjusting for covariates) for each of the binary outcomes: scheduled appointment within 2 weeks, completed appointment within 8 weeks, receipt of 1st dose of COVID vaccination (age 12-17 years) within 8 weeks, family member receipt of COVID vaccination within 8 weeks. We will do pair-wise comparison among the treatment groups and adjust p value of each comparison for multiplicity. If participants differ in potential covariates across treatment groups, we will conduct additional analyses adjusted for these variables. We will explore non-inferiority analysis for comparison the two groups that are expected to have similar appointment scheduled and completion rate in the MyChart trial.

We will also conduct per-protocol analyses according to the interventions actually received by the participants, recognizing that actual intervention received could be different from initial randomized intervention. For example, a parent allocated to group A might schedule an appointment after receiving the automated message and therefore would not receive a personalized contact attempt. In addition, we may explore potential interaction between the two interventions as a secondary analysis. All analysis will be conducted using SAS version 9.4.

Duration

The study will begin upon IRB approval and continue through December 31, 2022. During this time, we will discuss the significance of data, potential future projects and dissemination of results.

Process of Obtaining Consent

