Official Title of the study: **Effect of Varied Outreach Methods on Appointment Scheduling, Appointment Completion, and Receipt of MMR Vaccination**

NCT number: **NCT04567342**

Document name: **Statistical Analysis Plan**

Date of the document: **7/31/2023**

The results of the Outreach Methods study will be assessed as described in this document. This statistical analysis plan begins with an overview of the key components of the study, including its design, objectives, and outcomes measures. This is followed by a detailed description of the statistical analyses that will be utilized to address study hypotheses.

1. Overview of study: This study used a 2x2 factorial randomized control trial to test the impact of automated text/telephone messages and personal contact attempts on well child care (WCC) scheduling and completion and receipt of MMR vaccine. We randomized eligible patients to 1 of 4 groups: 1 automated message (Group 1), 2 automated messages (Group 2), 1 automated message plus personal contact attempts (Group 3), or 2 automated messages plus personal contact attempts (Group 4). We generated random allocation sequence stratified by clinic location using block randomization (with a block size of 4). Based on sample size calculations, we planned to enroll a minimum of 668 subjects overall aged 12-14 months old and 4 years old that met eligibility criteria based on data obtained from the electronic health record (EHR) from three academic pediatric primary care practices.

1.1 Study Objective: Test the effectiveness of text/telephone outreach messages and personal contact attempts on well child care (WCC) scheduling and completion and receipt of MMR vaccine.

Working hypothesis: Twenty percent of patients in Group 1, 35% of patients in Group 2, and 50% of those in Group 3, and 65% of those in Group 4 would receive the MMR vaccine by 15 months of age (for children who were 12-14 months old) or receipt of the second MMR dose by 3 months after first intervention (for children 4 years old).

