2.3.2 Primary outcome analysis

Primary outcome: Receipt of MMR by 15 months of age (for children who were 12-14 months old) or receipt of the second MMR dose by 3 months after first intervention (for children 4 years old).

- Receipt of MMR (yes or no) based on electronic health record documentation

For the primary outcome, we will use a modified Poisson regression models to estimate risk ratio (RRs) with statistical significance defined as 2-sided $p < .05$. If participants differ in potential covariates across treatment groups, we will conduct additional analyses adjusted for these variables.

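### The MyChart allocation unit is stated two ways and no trial has a sibling rule, so either spillover between arms or understated standard errors is possible, and the family-member outcome can be counted more than once

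*Protocol*

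**What the plan says.** The Protocol gives two allocation units for the MyChart trial. Under the factors under study: "Families enrolled in MyChart will be selected and randomized into the following groups". In the randomization paragraph for the MyChart and Televox trials: "randomly assign patients into one of the study groups as described above". Both Televox trials use the patient: "Patients will be randomized into the following three groups". So does the Personal Contacts trial, in the SAP overview: "We randomized eligible patients to 1 of 4 groups".

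The parent receives the message. The Protocol's automated-message paragraph says the platform will "send automated calls and text reminders to parents according to their preferences".

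One response variable belongs to the family: "Family member receipt of COVID vaccination in our health system within 8 weeks of first intervention". The Protocol's Analysis section lists it with the other MyChart and Televox outcomes, to be analysed "using logistic regression models (without adjusting for covariates) for each of the binary outcomes".

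Neither document keeps siblings together, limits entry to one child per household, excludes siblings, or names a household term or cluster. The SAP covers only the Personal Contacts trial. It plans modified Poisson regression and names no cluster unit.

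**The concern.** The parent is prompted and the parent books, but the child is analysed. The 6-11 and 12-17 age bands readily admit siblings. What goes wrong depends on which allocation sentence governs.

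- **Children allocated separately.** A parent prompted for one child may book both. That raises the response in the less intensive arm and shrinks the contrast. The Protocol also cancels a message if the parent books before it is sent, and arms are messaged in different weeks. A booking prompted through one sibling can therefore cancel the other sibling's intervention.
- **Families allocated.** Siblings share an arm, so within-trial spillover is avoided. Their outcomes are correlated, however, and a model that treats them as independent reports standard errors that are too small.
- **Either reading.** Siblings share relatives, so one relative's vaccination can be a success for two children. Those successes fall in one arm if families are allocated, and possibly in two arms if children are.

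**Working it through.** **1. The plan's own figures.** For two proportions, two-sided alpha 0.05, power 80%, pooled variance under the null:
n = [1.960·√(2p̄(1−p̄)) + 0.842·√(p1(1−p1)+p2(1−p2))]² / (p1−p2)².
- MyChart, 20% vs 30%: n = 293.2 (stated 293; 5 × 293 = 1465).
- Televox 12-17, 30% vs 40%: n = 355.9 (stated 356; 3 × 356 = 1068).

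These are sizes for independent children, with no allowance for households.

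**2. How often siblings are split under child allocation.** With k equal groups the probability of different arms is 1 − 1/k. That is 1 − 1/5 = 80% for MyChart and 1 − 1/3 = 67% for Televox.

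**3. Spillover under child allocation.** Suppose a share c of the lower arm responds at the higher arm's rate, so the lower rate becomes p1 + c(p2 − p1). For 20% vs 30% at 293 per group:

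| c (assumed) | Lower-arm rate | Power |
|---|---|---|
| 0 | 20.0% | 80% |
| 5% | 20.5% | 76% |
| 10% | 21.0% | 71% |
| 20% | 22.0% | 60% |

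To place c, let f be the share of children with a sibling in the same trial, and assume f = 10% to 30% with full carry-over. If only a sibling in the one comparison arm matters, c = f/5 = 2% to 6%. If a sibling in any of the four message arms matters, c = 0.8f = 8% to 24%.

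For the no-message arm, with carry-over s of 0.5 to 1, the rate is 0.02 + f × 0.8 × s × (0.20 − 0.02). This gives 2.7% (f = 0.1, s = 0.5) to 6.3% (f = 0.3, s = 1), against the planned 2%.

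**4. Variance under family allocation.** If siblings come in pairs, the design effect is 1 + f × ICC. With f = 10% to 30% and ICC 0.3 to 0.5 (both assumed), it runs from 1 + 0.1 × 0.3 = 1.03 to 1 + 0.3 × 0.5 = 1.15.

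| | Plan | × 1.03 | × 1.15 | Eligible now |
|---|---|---|---|---|
| MyChart, per group (total) | 293 (1465) | 302 (1510) | 337 (1685) | 1000, replications planned |
| Televox 6-11 | 293 (879) | 302 (906) | 337 (1011) | 2500 |
| Televox 12-17 | 356 (1068) | 367 (1101) | 410 (1230) | 1100 |

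At the planned sizes, power would be about 79% to 74%, and the type I error of an unclustered test about 0.054 to 0.068. For the family outcome, ICC is near 1 and the factor is about 1.1 to 1.3.

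**5. Whether both harms occur together.** A simulation of the unclustered test (20,000 runs, 40% of children in sibling pairs, ICC 0.5 and 0.8, all assumed) gave type I error 0.076 and 0.089 with family allocation, but 0.052 and 0.051 with child allocation. The variance problem therefore belongs to the family reading and the spillover problem to the child reading.

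**The case against.** A reader might infer that the arms are contaminated and the standard errors are also wrong. The documents do not support that combined claim. The MyChart sentence that names families, read literally, keeps siblings together. If children are allocated separately instead, ignoring the household leaves the type I error near 5%.

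Contamination is also a risk and not a shown fact. Each TeleVox script names one child, and the sibling share, carry-over and ICC are all assumed.

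The lead MyChart test is hardly touched. With the no-message rate at 6.3%, power for 6.3% vs 20% at 293 per group is still about 99.9%. What spillover can damage is the size of that estimate and the narrower contrasts that set the sample size.

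The scope has limits too. The designated primary outcome, MMR, belongs to Personal Contacts. That trial has no no-message arm and no family outcome, and its age bands (12-14 months and 4 years) are narrow, so few co-eligible siblings are expected. The family outcome is one non-primary outcome.

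All of this stands, and it limits the size of the point. It does not remove the conflict over the unit, the missing sibling rule or the undefined counting of the family outcome.

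**Conclusion.** The point holds as a conditional one. The MyChart unit is contradictory, and no trial has a sibling rule or a household term. Each reading of the unit has its own cost:
- **Child allocation:** possible dilution, with power for 20% vs 30% falling from 80% to about 76% to 60% if 5% to 20% of the lower arm is affected.
- **Family allocation:** understated standard errors, with a design effect of about 1.03 to 1.15 for child outcomes.

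These sizes rest on assumed sibling shares, carry-over and ICCs, because the documents give none. The family-member outcome is the firmest part. It needs no spillover assumption, only siblings in the same trial who share relatives.

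**What to change.** 1. Reconcile the two MyChart passages to one allocation unit. For MyChart and Televox, the household (shared parent contact or MyChart account) is preferable if allocation is not yet done. The documents do not say whether these trials have been run. If they have, report the unit actually used.
2. Use household-clustered robust variance in the MyChart and Televox logistic models. In the Personal Contacts modified Poisson models, add it as a sensitivity analysis.
3. Define which relatives count as family members, and analyse that outcome once per household. If siblings were already split across arms, use one prespecified index child per household. This stops double counting but does not undo spillover.
4. Report the number of households with more than one randomized child, and restate power with a stated design effect.

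The cost is a household identifier in the EHR report, a cluster statement in the models, and a slightly smaller effective sample size. For Televox 12-17 this matters: even a design effect of 1.03 gives 3 × 367 = 1101, one more than the 1100 eligible, so the plan must accept slightly lower power or recruit further. Household allocation within one trial also leaves a possible route between trials. The three trials run one after another over weeks 1 to 10 with 8-week completion windows, so siblings in different age bands may still be exposed.

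### MyChart and Televox trials: the no-message arm and the message arms are timed from different start dates, and some outcomes have no start date for the no-message arm

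*Protocol*

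**What the plan says.** The Protocol's list of response variables (section 2) times visit completion over eight weeks from the intervention, then adds an exception: "Appointment completed within 8 weeks of randomization will be used for group who does not receive any intervention". Only the MyChart trial and the two Televox trials have such a group. Every arm of the Personal Contacts trial gets at least one automated message.

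The exception is attached to completion alone. Scheduling is judged "within 2 weeks of intervention (Y/N) (date of actual appointment may be greater than 2 weeks from intervention". The two vaccination outcomes read "Receipt of 1st COVID vaccination (ages 12-17 years) within 8 weeks of first intervention (Y/N" and "Family member receipt of COVID vaccination in our health system within 8 weeks of first intervention". None of these three has a rule for an arm without an intervention, although the Analysis section lists all of them for the MyChart and Televox trials.

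On timing, the randomization paragraph for these trials says: "Groups will receive their assigned intervention in one of four successive weeks with the sequence randomly assigned (see table below". The calendar is "Weeks 1-3 = Televox Trial 12-17yo, Weeks 4-7 = Televox Trial 6-11yo, Weeks 8-10 = MyChart Trial". Within a trial the message conditions carry different week labels. In Televox 6-11, for example, one arm is "2 automated standard messages sent (e.g. Thu, Fri) (weeks C, C" and the other "2 automated tailored messages sent (e.g. Thu, Fri) (weeks D, D". The note after those tables says that a family who books between randomization and contact is not contacted. The Analysis section specifies intent-to-treat. The SAP (section 1, Overview of study) describes only the four-group trial, so it does not address any of this.

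**The concern.** A randomized comparison relies on both arms being observed over the same period. Here the control arm's clock starts at randomization and a message arm's clock starts at contact, which can be later. The compared proportions then come from different stretches of calendar time and different distances from the eligibility report. Any difference between those stretches enters the estimated message effect.

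Two gaps add to this. For scheduling and COVID vaccination, the analyst has to choose a control start date that the plan does not give. For message-arm families who book before contact, there is no intervention date from which to score any outcome, while a control family who books on the same day can simply be counted. MyChart's test of two messages against none matters most, because it opens the fixed testing sequence (Power/Sample Size, MyChart Trial).

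**Working it through.** **1. The plan's own figures.** Pooled two-proportion formula, two-sided alpha 0.05 (sidedness assumed), power 80%:

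n = [1.960·√(2p̄q̄) + 0.842·√(p₁q₁ + p₂q₂)]² / (p₁ − p₂)²

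- 20% vs 30%: 293.2 per group (stated 293).
- 30% vs 40%: 355.9 per group (stated 356).

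Both are driven by message vs message differences, so the control arm's start date does not enter them.

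**2. The windows.** Let d be the days from randomization to an arm's contact.

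- Control, completion: days 0 to 56. Message arm: days d to d + 56. Shared days: 56 − d.
- Scheduling, if controls were also dated from randomization: days 0 to 14 against d to d + 14. Shared days: max(0, 14 − d).

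**3. What d can be.** The documents do not give it. If all groups in a trial are randomized together, message conditions in different weeks cannot all be contacted on the day of randomization, so at least one has d above 0. Which one is not fixed, because the week order is random. For illustration, assume randomization on the Monday of the trial's first calendar week and the example weekdays in the tables. Then d is:

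- MyChart (Monday, three weeks): 0, 7 or 14.
- Televox 12-17 (Thursday, three weeks): 3, 10 or 17.
- Televox 6-11 (Thursday, four weeks): 3, 10, 17 or 24.

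**4. Overlap.**

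| d (days) | 8-week window, shared of 56 | 2-week window, shared of 14 |
|---|---|---|
| 0 | 56 | 14 |
| 7 | 49 | 7 |
| 10 | 46 | 4 |
| 14 | 42 | 0 |
| 17 | 39 | 0 |
| 24 | 32 | 0 |

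**5. Whether the shift changes a rate.** If the background visit rate is flat and early bookings are treated alike, two windows of equal length have equal expected counts, so the bias is zero at every d. The plan secures neither condition.

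- *Upward.* Eligibility removes children with a visit booked in the next 45 days. Visits already booked further ahead can fall on 11 days of the control window (46 to 56) but on 11 + d days of the message window. Take the plan's 2% control rate, no true effect, and an assumed share s of that 2% that was pre-booked. The shift is 2% × s × d/11. For s from 0 to 50% it is 0 to 0.6 points at d = 7, 0 to 1.3 at d = 14 and 0 to 2.2 at d = 24.
- *Downward.* If visits before contact are lost from the message arm and not replaced, the shift is −2% × d/56: −0.25 points at d = 7, −0.5 at d = 14 and −0.9 at d = 24.

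The documents give no value for s, so these are illustrations only.

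**6. Against the planned effects.** Two messages vs none on completion: 20 − 2 = 18 and 30 − 2 = 28 points (MyChart, Televox 6-11); 30 − 2 = 28 and 40 − 2 = 38 (Televox 12-17). The smallest planned message vs none difference is 10 − 2 = 8 points (one standard MyChart message).

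**The case against.** The strongest reply is that both windows are eight weeks long, so nothing is gained or lost by moving one. That is right under a flat background with equal handling of early bookings, and it is why no bias can be asserted. It does not settle the matter, because the eligibility rule makes pre-booked visits uneven over time and the plan has no rule for families who book before contact.

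A second reply is that randomization is the natural start for the untreated arm on every outcome. For scheduling, that reading makes the comparison worse, as the overlap table shows.

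A third is that the effect is small beside the planned differences. This stands for completion and limits how serious the point is.

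A reader might go further and infer that every message vs no-message contrast is misaligned. The documents do not support that: the week order is random and the delay unstated, so a MyChart arm contacted on the day of randomization would have identical windows. A reader might also infer that false-positive rates are inflated in favour of messages. That does not follow either. It would need a delay and a pre-booked share that the plan does not give, and plausible assumptions move the rate in either direction.

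**Conclusion.** The inconsistency is in the text and should be corrected. The completion rule gives compared arms different time origins whenever contact follows randomization. The scheduling and COVID outcomes lack a control origin. Families who book before contact lack any origin.

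Direction and size of bias are not determined. On the assumptions shown, the completion shift runs from about −0.9 to +2.2 points. That is unlikely to overturn planned differences of 18 to 38 points, and would matter mainly if true effects are small. Two-week scheduling is the most exposed outcome, because the delay can equal or exceed its whole window. The sample sizes of 293 and 356 per group are unaffected. So is the MMR outcome, which belongs to the trial without a no-message arm. The text is certain; the days of delay and the rate shifts are assumptions.

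**What to change.** Replace the sentence on the untreated group with one index-date rule covering all arms and all timed outcomes:

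- For each message vs no-message comparison, the index date is that message arm's assigned contact date. It applies to every child in both arms, whether or not a message was sent.
- All randomized children stay in the denominator.
- Appointments booked or completed, and vaccinations received, between randomization and the index date are handled identically in both arms, for example as events in both. Each arm is then observed from randomization to the same end date: d + 56 days for the eight-week outcomes and d + 14 for scheduling.

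In MyChart, both two-message cells are in Week B, so one control date serves the first-step test.

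The cost is wording and programming on dates already in the health record, with no added patients, contacts or randomization. The scheduled contact date must be retained for each arm. Separate two-arm comparisons are needed where message arms have different weeks, because the controls then carry a different date in each. Counting every arm from randomization for the original 56 or 14 days would be simpler, but it leaves message arms only 56 − d days after contact and, for scheduling, none once d reaches 14.

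### Televox arms and the MyChart 1- and 2-message arms are messaged in different weeks, so those contrasts cannot be separated from delivery week; in Personal Contacts the confounding is partial

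*Protocol*

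**What the plan says.** The protocol's Randomization paragraphs, both for Personal Contacts and for MyChart and Televox, state: "Groups will receive their assigned intervention in one of four successive weeks with the sequence randomly assigned". The week tables then give each arm its own slot.

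- **Personal Contacts:** three four-week replicates, with each of weeks 1-12 used by exactly one arm. For example, 2 messages alone is "Message sent on Thu & Fri (weeks 4, 6, 12" and 2 messages + contact is "of following week (weeks 1, 8, 9".
- **MyChart:** both 1-message arms in Week A and both 2-message arms in Week B.
- **Televox 6-11:** the low arm is "2 automated standard messages sent (e.g. Thu, Fri) (weeks C, C" and the high arm is weeks D, D. The labels are not explained.
- **Televox 12-17:** the low arm is week A, against "COVID Tailored Message 2 automated messages sent (e.g. Thu, Fri) (week B".

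Outcome windows for messaged arms run from the intervention. For untreated children: "Appointment completed within 8 weeks of randomization will be used for group who does not receive any intervention". The infant MMR deadline is fixed at 15 months of age. For 4-year-olds the protocol has "receipt of 2nd MMR dose by 3 months after randomization (Y/N", while SAP 1.2 counts the three months from first intervention.

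The protocol's main models are logistic regressions without covariates, with pairwise p values adjusted for multiplicity. SAP 2.3.2, which covers Personal Contacts only, uses modified Poisson regression. Neither has a week, replicate or delay term. Appointment access at first message and the community COVID rate appear in the protocol's covariate list. They enter only additional analyses if groups differ, and SAP 2.3.1 does not list them.

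**The concern.** Individual randomization balances the children but not the week in which an arm is contacted. If one arm is contacted in one week and its comparator in another, anything that moves uptake that week moves the arm contrast: appointment supply, school holidays, COVID news. The standard error counts children and omits variation between weeks.

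The exposed contrasts are central ones. Low vs high and low vs COVID tailored determine the Televox sample sizes. 2 vs 1 message is the second step of MyChart's fixed sequence. Contrasts with no message also cover different calendar periods, because the untreated window starts at randomization.

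The listed covariates do not repair this with one week per arm. An area-wide COVID rate at the message date has one value per arm, and one at randomization has the same value in all arms. Appointment access helps only through clinic-by-week differences.

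Personal Contacts has a second route. With a deadline fixed by age, an infant in a later arm has less time left after the message. This matters only as far as messages prompt vaccination. The protocol itself foresees some families acting first: "automated messages and/or personal contact attempts will not be completed if the parent schedules an appointment after being randomized but before receiving the intervention".

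**Working it through.** **1. Which active-arm pairs differ in week.** Personal Contacts 6 of 6 (within every replicate), MyChart 4 of 6, Televox 6-11 1 of 1, Televox 12-17 1 of 1. MyChart low vs high tailoring at the same message count shares a week and is clean.

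**2. The plan's own figures.** n = [1.96√(2p̄(1−p̄)) + 0.84√(p₁(1−p₁)+p₂(1−p₂))]² / (p₁−p₂)². For 20% vs 30% this gives 293.2 (protocol 293), and for 30% vs 40% it gives 355.9 (protocol 356). The Televox sizes therefore come from contrasts between two delivery weeks or week pairs.

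**3. Estimability in Personal Contacts.** Arm plus a 12-level week has 15 columns but rank 12, so arm is not estimable given calendar week. Arm + replicate + position within replicate has 9 columns and rank 9, so arm is estimable given those. Delay = (week−1) mod 4:

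| Arm | Weeks | Delays | Mean delay (weeks) |
|---|---|---|---|
| 1 message | 3, 5, 10 | 2, 0, 1 | 1.0 |
| 2 messages | 4, 6, 12 | 3, 1, 3 | 2.3 |
| 1 + contact | 2, 7, 11 | 1, 2, 2 | 1.7 |
| 2 + contact | 1, 8, 9 | 0, 3, 0 | 1.0 |

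**4. Delay shift in infants (all inputs assumed).** Every arm is given the same message effect, so any difference comes from delay alone. P = 0.5 × mean of [1 − exp(−L(r·pre + post))], where L = ln 2/(7 × m) per day and m = 2, 4 or 8 weeks. T is days from the first slot to 15 months of age, pre = min(delay, T), post = max(T − delay, 0), and r is the pre-message rate relative to the post-message rate. Ages are uniform from 12 to 14 or to just under 15 months, with or without trials 2-3 limited to 12.0-12.9 months.

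Example: age 13 months, T = 60.9 days, m = 4, r = 0, L = 0.02476. Delays of 0/1/2/3 weeks give 38.9/36.8/34.3/31.4%. Then 2 + contact = (38.9+31.4+38.9)/3 = 36.4%, 2 messages = (31.4+36.8+31.4)/3 = 33.2%, and 1 message = (34.3+38.9+36.8)/3 = 36.7%. The spurious differences are +3.2 points (2 + contact minus 2 messages) and −3.5 (2 messages minus 1 message).

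Over the full grid, equal replicates:

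| Contrast (planned difference) | r = 1 | r = 0.5 | r = 0 |
|---|---|---|---|
| 2 + contact − 2 messages (30) | 0 | +0.9 to +2.0 | +2.3 to +5.0 |
| 2 messages − 1 message (15) | 0 | −0.6 to −1.9 | −1.7 to −5.0 |

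**5. True error of an unadjusted 5% test (week SDs assumed).** Error = 2[1 − Φ(1.96·SE/√(SE² + 2·SD²(1−ρ)Σw²))], where w is each week's share of an arm. SE = √(2 × 0.35 × 0.65/356) = 3.58 points for Televox 12-17, √(2 × 0.25 × 0.75/293) = 3.58 for n = 293, and √(2 × 0.25/167) = 5.47 for Personal Contacts.

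| Weeks per arm | ρ | SD 1 | SD 2 | SD 3 | SD 5 |
|---|---|---|---|---|---|
| One (n = 356 or 293) | 0 | 7% | 12% | 21% | 38% |
| One | 0.8 | 5% | 6% | 8% | 14% |
| Two (n = 293) | 0 | 6% | 9% | 13% | 25% |
| Personal Contacts, equal replicates | 0 | 5% | 6% | 7% | 12% |
| Personal Contacts, trial 1 holds 78% | 0 | 5% | 7% | 9% | 17% |

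**The case against.** A reader might infer from the count in step 1 that 12 of 14 active contrasts are equally compromised, the primary MMR result included. The documents do not support that. Six of the 12 are Personal Contacts pairs, where the order is re-randomized over three replicates. That gives no built-in direction, and arm stays estimable given replicate and delay. Error there is near nominal at SDs of 1-3 points with equal replicates.

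A reader might also take 21-38% as the expected error. Those figures need independent weeks with SDs of 3-5 points, which is hard to square with a planned no-message completion rate of 2% unless response to messages itself varies by week. If deliveries are one week apart, the 8-week windows share seven of eight weeks, which favours the lower figures for background effects. A shock to response in one delivery week could still be independent.

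The error rates are also for an unadjusted test, while the protocol adjusts pairwise p values. Assuming Bonferroni over three Televox 12-17 pairs, one week per arm gives 2.6/6.0/12.3/28.0% (independent) or 1.8/2.4/3.4/7.3% (correlation 0.8) against a nominal 1.7%. The levels fall, but the inflation stays.

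Finally, weeks C, C and D, D may mean two weeks per arm, and the protocol expects two MyChart replications. Varying the order over replications would ease the problem, but no such order is given. None of these points separates arm from week in the schedule as written.

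**Conclusion.** The concern holds in limited form. For Televox 12-17, Televox 6-11 and MyChart 1 vs 2 messages, the scheduled contrast cannot be separated from delivery week unless the order is varied over replications. That follows from the week tables and needs no assumption. Its size does: the documents give no between-week SD or correlation, so the excess error could be negligible or large.

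In Personal Contacts the confounding is partial. With equal replicates, the published order favours 2 + contact over 2 messages in infants by 0 to about 5 points (1-2 at half the pre-message rate) against a planned 30, and makes 2 vs 1 message 0 to 5 points too low against a planned 15. If messages do not change the vaccination rate, the delay causes no bias in infants. These ranges rest on an assumed 50% ceiling, assumed speed of response and assumed ages. They do not show that the primary comparison is invalid.

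**What to change.** **Any trial or replicate not yet delivered.** Within clinic and replicate, randomize children to delivery week independently of arm, so that every week carries a share of every arm. Give no-message children a matching index week that starts their window, and fit delivery week as a stratum. The cost is several short message lists per week and one model term. Message content and total contacts do not change.

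**If all trials are delivered**, as the SAP date (7/31/2023) and the protocol's stated end (December 31, 2022) suggest:

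- *Televox and MyChart.* Report different-week contrasts that rest on one week per arm as confounded with calendar week. Beside them, show the no-message children's outcome counted from each delivery week in turn, and the difference between weeks. At the planned 2% rate its standard error is at most about √(2 × 0.02 × 0.98/356) = 1.05 points, treating the windows as independent. It checks background effects only, not week differences in response to messages.
- *Personal Contacts.* Add one sensitivity model in 12-14-month-olds with replicate, age at randomization and scheduled (not actual) delay. The standard error for 2 + contact vs 2 messages is 11% wider with equal replicates (variance ratio 1.24; √1.24 = 1.11) and about 60% wider if trial 1 holds 78% of children. The model does not add between-week variance, and the report should say so.

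**Separately**, reconcile the protocol and the SAP on whether the 4-year-old window starts at randomization or at first intervention.
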